4.2. Exclusion Criteria

Subjects that meet any of the following exclusion criteria will be excluded from participating in the study:

General

1. Major surgery (including joint surgery) within 12 weeks prior to screening or planned within 12 months after dosing

Medical Conditions

- 2. History of or current inflammatory joint disease other than RA or other autoimmune or inflammatory disease that may confound clinical assessments or increase subject risk in the study
- 3. Current or previous (within the past two years) evidence of serious uncontrolled concomitant cardiovascular, pulmonary (including obstructive pulmonary disease), renal, hepatic, endocrine (including uncontrolled diabetes mellitus) or gastrointestinal disease
- 4. Active current infection or history of recurrent bacterial, viral, fungal, mycobacterial or other infections, including but not limited to tuberculosis and atypical mycobacterial disease, hepatitis B and C, and herpes zoster (>2 episodes within the previous 12 months)
- 5. Any major episode of infection requiring hospitalization or treatment with IV antibiotics within four weeks of screening or oral antibiotics/anti-infectives within two weeks prior to screening
- 6. Active tuberculosis requiring treatment within three years prior to screening
- 7. Latent tuberculosis diagnosed during screening that has not been appropriately treated

- 8. Primary or secondary immunodeficiency (history of or currently active), including a history of HIV positivity
- 9. Prior diagnosis with diverticulitis requiring antibiotic treatment
- 10. Females who are pregnant or breastfeeding or planning to become pregnant within 12 months from start on study
- 11. History of malignancy within five years from the time of screening (including squamous cell carcinoma of the skin or cervix or carcinoma-in-situ), except adequately treated basal cell carcinoma
- 12. History of epilepsy or other seizure disorder, stroke, dementia or other central nervous system disorder
- 13. Known history of drug or alcohol abuse within one year of screening
- 14. Any medical or psychological condition that in the judgment of the Principal Investigator would interfere with the conduct of the study or may confound the interpretation of the study results
- 15. Any out-of-range electrocardiogram (ECG) parameter(s) or abnormal finding(s) considered clinically significant by the Investigator including if the QTc calculated using Fridericia's formula (QTcF) is:
 - >450 ms in males or >470 ms in females

Excluded previous or concomitant therapy

- 16. Prior treatment with cell or gene therapy
- 17. Treatment with an investigational agent within 30 days or five half-lives, whichever is longer prior to screening
- 18. Treatment with intravenous, intra-articular or intramuscular glucocorticoids within 14 days of the screening visit
- 19. Treatment with azathioprine, cyclophosphamide, cyclosporine, leflunomide, and sulfasalazine within 4 weeks of the screening visit:
 - Subjects previously on leflunomide must have either discontinued ≥8 weeks prior to screening or discontinued with the following elimination procedure at least 4 weeks prior screening
 - Cholestyramine or activated charcoal should be taken at standard doses for a minimum of 6 days but ideally for the standard 11 days (Arava ® U.S. Package Insert, 2011)
- 20. Treatment with abatacept or rituximab within 3 months of the screening visit

Prior/Concurrent Clinical Study Involvement

21. Is currently participating in another trial of an investigational or marketed drug or medical device

Allergies/Anaphylaxis

- 22. Any confirmed clinically significant drug allergy and/or known hypersensitivity to protein therapeutics or formulation components or a related drug
- 23. Known allergy to heparin, fresh frozen plasma (FFP) or replacement colloid/albumin

Specific Laboratory Assessments

- 24. Laboratory tests, if abnormal, may be repeated once during the screening period. Clinically significant abnormalities in laboratory test results that would exclude a subject from study participation include:
 - a) AST or ALT $>2 \times$ the upper limit of normal (ULN)
 - b) Total and direct bilirubin >1.5 x ULN
 - c) EGFR <45 ml/min/m² (2021 CKD-EPI criteria; (Delgado, et al., 2022)
 - d) Absolute neutrophil count <1.0 x 10⁹/L
 - e) Platelet count $<100 \times 10^9/L$
 - f) Hemoglobin <9 g/dL
 - g) Positive hepatitis BsAg or hepatitis C antibody

Note: In the event of a potential false positive hepatitis C antibody test result, PCR testing for HCV RNA may be performed; subjects who are negative for HCV RNA by PCR are not excluded

Other Exclusions

- 25. Donation of blood or clinically significant loss of blood, in the opinion of the Investigator, within three months prior to date of consent
- 26. Subjects under judicial supervision or guardianship

4.3. Screen Failures

Individuals who do not meet the criteria for participation in this study (screen failure) may be rescreened. Subjects may be rescreened up to two times, if deemed appropriate by the Principal Investigator. All screening assessments that led to screen failure must be repeated for rescreening.

During the course of screening if a lab result is not available for technical reasons (e.g., blood sample hemolysis), this evaluation may be repeated, and this will not be considered a rescreen. A lab result (other than those specified in the exclusion criteria) outside the normal range will be considered as a reason to screen fail if it is deemed clinically significant, in the opinion of the Investigator.

5. CONCOMITANT THERAPY

Concomitant therapy consists of any general medication used by a subject in addition to SBT777101 from 30 days prior to screening to the end of the study/early termination visit.

Prior and current therapies used by a subject for the treatment of RA must be reported from the time of diagnosis through to the end of the study/early termination visit, where available. This includes DMARDs and corticosteroids. Pain medications used to manage signs and symptoms of RA are considered general medications and must be recorded for the 30 days prior to screening.

Please contact the Medical Monitor for guidance on management of concomitant medications, including medications for RA and rescue therapy.

5.1. General Medications

Standard medications are permitted for the treatment of general medical conditions during the screening, pre-treatment and treatment periods of the study.

- Medications should be kept at stable doses from 30 days prior to screening throughout the study where possible.
- Receipt of new medications required for synovial biopsy, synovial fluid collection, apheresis and infusion are permitted.
- If corticosteroids are required for reasons other than RA, appropriate doses should be administered (e.g., ≤10 mg/day PO prednisone or equivalent) for no more than two weeks and should be tapered down to the previous level as rapidly as medically possible.

5.1.1. Vaccines

- Subjects who have received a vaccine should have completed their vaccination schedule at least two weeks prior to dosing
- Live vaccines are not permitted during the study
- COVID-19 vaccination including at least one booster is recommended

5.2. Medications for RA

Certain concomitant medications for the treatment of RA are permitted or prohibited. Details on medication types, doses and management of treatments are provided in the sections below.

5.2.1. Permitted Medications for RA

Details of the potential impact of permitted concomitant medications for RA with SBT777101 are provided in Appendix H.

The following medications are permitted during the study up to Week 48. Guidance on doses and routes of administration are provided below:

- NSAIDs (see Table 2 for guidance)
- Pain relief medications (see Table 2 for guidance)
- Oral corticosteroids (see Table 2 for guidance)
- csDMARDs (see Table 2 and Table 3 for guidance)

- o Methotrexate (≤25 mg SC, PO or IM QW)
- o Hydroxychloroquine (200 mg PO BID or 400 mg PO QD)
- bDMARDs (and biosimilar equivalents) (see Table 2 and Table 3 for guidance
 - o Adalimumab (40 mg SC QW or Q2W)
 - o Golimumab (50 mg SC once monthly)
 - o Infliximab (3-10 mg/kg IV Q4W Q8W)
 - o Certolizumab pegol (200 or 400 mg SC Q2W)
 - Etanercept (50 mg SC QW)
 - o Anakinra (100 mg SC QD)
 - o Tocilizumab (162 mg SC QW or Q2W; 4 or 8 mg/kg IV Q4W)
 - o Sarilumab (200 mg SC Q2W)

5.2.2. Prohibited Medications for RA

Details of the potential impact of prohibited concomitant medications for RA on SBT777101 are provided in Appendix I.

Use of the following medications is prohibited during the study from screening to Week 48:

- Intramuscular corticosteroids
- Intravenous corticosteroids
- Intraarticular corticosteroids
- csDMARDs
 - o Azathioprine
 - Cyclophosphamide
 - Cyclosporin
 - o Leflunomide
 - Sulfasalazine
- bDMARDs (and biosimilar equivalents)
 - Abatacept
 - o Rituximab

tsDMARDs must be discontinued at least 7 days prior to the subject undergoing apheresis and are prohibited to Week 48.

- tsDMARDs
 - o Baricitinib
 - Filgotinib

- o Tofacitinib
- o Upadacitinib

5.2.3. Guidelines for the Management of Medications for RA

It is important that doses of medications taken for the treatment of RA remain stable throughout the study where possible. If clinically required for safety reasons or to manage disease activity, modifications to the treatments are allowed and are described in Table 2 below.

Table 2: Guidelines for Use of Certain Medications for RA During the Study

Medication	Guidance	
Screening (first study visit through enrollment)		
DMARDs	Doses must remain stable during screening Subjects should not start a new DMARD or switch to a different type of	
	DMARD at any time	
Oral corticosteroids	Subjects may receive background treatment (≤10 mg/day prednisone or equivalent)	
	If changes in dose are required, the increased dose must be no higher than 20 mg/day and must be tapered quickly, returning to the previous dose level within 2 weeks	
NSAIDs	NSAIDs (e.g., ibuprofen and naproxen) are permitted	
Pain relief medications	Short courses of pain relief medications (e.g., opioids and acetaminophen) are permitted.	
Pre-treatment period (apheresis through study drug administration)		
DMARDs	Doses must remain stable during pre-treatment up to study Day 1	
	Subjects should not start a new DMARD or switch to a different type of DMARD at any time	
Oral corticosteroids	Subjects may receive background treatment (≤10 mg/day prednisone or equivalent)	
	The dose must remain stable for at least 1 week before the synovial biopsy procedure and/or synovial fluid collection.	
	If changes in dose are required, the subject must return to the previous dose level within 2 weeks and remain at that stable dose for at least 7 days before the study Day 1 visit can occur.	
NSAIDs	NSAIDs (e.g., ibuprofen and naproxen) are permitted but should not be used in the 7 days prior to the synovial biopsy collection where possible	
Pain relief medications	Short courses of pain relief medications (e.g., opioids and acetaminophen) are permitted.	

Table 2: Guidelines for Use of Certain Medications for RA During the Study (Continued)

Medication	Guidance	
Safety follow-up period (Day 1 through Week 48)		
DMARDs	Doses must remain stable during the safety follow-up period	
	Subjects should not start a new DMARD or switch to a different type of DMARD	
Oral corticosteroids	Subjects may receive background treatment of corticosteroids (≤10 mg/day prednisone or equivalent)	
	The dose must remain stable for at least 1 week before the synovial biopsy procedure and/or synovial fluid collection and the Week 12 study visit	
	If changes in dose are required, the increased dose must be no higher than 20 mg/day and must be tapered quickly, returning to the previous dose level within 2 weeks	
NSAIDs	NSAIDs (e.g., ibuprofen and naproxen) are permitted but should not be used in the 7 days prior to the post dose synovial tissue collection where possible.	
Pain relief medications	Short courses of pain relief medications (e.g., opioids and acetaminophen) are permitted.	

5.2.4. Rescue Therapy

Certain concomitant medications are permitted as rescue therapy for the treatment of RA flares. Rescue therapy is permitted if a subject experiences ≥30% worsening in TJC and/or SJC compared to study Day -10 to -4 according to the guidance provided in Table 3 below. Rescue therapy must not be given until all assessments have been completed at a study visit.

Table 3: Rescue Therapy Guidelines

Medication	Guidance
DMARDs	Increase doses of existing permitted DMARD to a higher approved dose after Week 12
	Start a new DMARD or switch to a different type of DMARD after Week 12
Oral corticosteroids	Increases in corticosteroid dose up to 20 mg/day are permitted after Week 12. The dose must be tapered, returning to the previous dose level, within 4 weeks
Intraarticular corticosteroids	May be used in a limited fashion as treatment for severe RA flares after Week 12.

5.2.5. Use of Prohibited Medication

Use of prohibited medication is not allowed during the study from screening to Week 12 (see Section 5.2.2 for details of prohibited medications). However, if a subject does take a prohibited medication or receives rescue therapy outside of permitted guidelines they should remain in the study and continue to attend visits and complete study assessments as described in the SoA (Appendix B).

6. STUDY DRUG

6.1. Description of Study Drug

SBT777101 is a suspension of autologous human regulatory T cells (T_{regs}) expressing a CAR transmembrane protein, which targets citrullinated proteins including CV in the extracellular domain of subjects with inflammatory diseases.

Peripheral blood cells are removed from an RA patient through apheresis. The apheresis product is enriched for CD25⁺ cells through cell selection followed by cell sorting for CD4⁺CD127^{lo/-}CD25⁺ cells using a microfluidics chip-based cell sorter. After cell selection and sorting, the cells are placed into in vitro culture and activated using anti-CD3/CD28 magnetic beads. Following activation and cell recovery, a lentiviral vector encoding the construct for the citrullinated protein-specific CAR, is added to the culture, and cells are subsequently expanded in serum free media containing IL-2. The cells are restimulated on Day 9 with anti-CD3/CD28 beads and expanded until Day 14. The cells are then harvested, washed and formulated in a cryopreservation solution with a targeted cell density of 30 x 10⁶ cells/mL. Upon formulation, cells are filled into cryobags and cryopreserved using a controlled-rate freezer. The Drug Product (in bags) is shipped under qualified conditions to the clinical site and thawed prior to administration to the patient.

Procedures will be in place to address product tracking requirements, including collection of the apheresis product, receipt of the apheresis product for manufacturing, SBT777101 manufacturing and testing, labeling, and packaging for shipment. The identity of the product will be checked and verified at each step of the cell apheresis, manufacturing, shipping, and administration process.

6.2. Product Labeling

Each SBT777101 infusion bag label will contain, at a minimum, the following information:

- Subject name (first and last)
- Subject date of birth
- Protocol Number
- Unique sponsor assigned product order tracking number
- Unique Subject Identifying Number (Subject ID)

These identifiers listed above are maintained throughout order management/scheduling, apheresis collection procedure, the manufacturing process and at infusion and are documented on the final product labels prior to cryopreservation.

6.3. Storage and Shipping

The cryopreserved SBT777101 final product will be stored in a continuously monitored vapor-phase liquid nitrogen freezer designed to maintain a temperature of ≤-150°C. The final product will be transported in a qualified liquid nitrogen dry vapor shipper, which is designed to maintain temperature for at least 10 days. The product will be shipped via a sponsor managed and qualified courier with continuous data loggers, monitoring, and chain of custody documentation.

Details on storage, handling, and preparation of SBT777101 are provided in the Investigational Product Manual.

6.4. Drug Accountability

In accordance with GCP, the study site will account for all supplies of product SBT777101. Details of receipt, storage, assembly, infusion, and destruction or return are provided within Investigational Product Manual.

The Principal Investigator or their representative will account for drug product provided by the Sponsor. All drug products are required to be stored at the site in a secure and locked location. The Principal Investigator shall maintain adequate records of the disposition of the drug product including dates, quantity and use by subjects.

6.5. Drug Disposal and Destruction

Any unused product that remains in the unopened shipper and is still within the product stability window may be returned to the Sponsor (e.g for research purposes). Return of product to the manufacturing site should be coordinated with the Sponsor.

Any used or unused product that has exceeded the product stability window and all unused administration supplies must be disposed of in accordance with the policy at the clinical site.

6.6. Dosing Regimen

A single dose of SBT777101 study drug will be administered to the subject by intravenous infusion (see Table 1 for planned doses).

6.7. SBT777101 Preparation and Cell Thaw

The SBT777101 shipping container must be opened, and the thaw commenced on a date prior to the packaging expiration date on the shipper.

The product is removed from LN2 shipping container and visually inspected to ensure that there is no leakage or damage and identity of the product verified for the intended Subject.

SBT777101 is supplied in sealed cryobags; the number of bags supplied for each subject will differ depending on the dose level and the number of transduced cells present in the product. The Sponsor will provide the exact volume of study drug to be infused for each individual subject.

Please refer to the Investigational Product Manual for details on preparation and thaw of SBT777101.

6.8. SBT777101 Administration

Prior to administration, the drug product should be visually inspected. SBT777101 should only be administered by trained and qualified study staff in a setting equipped for the safe administration of a cell therapy product.

A calculated volume of SBT777101 based on dose assignment will be administered to the subject. Prior to infusion, the identity of the subject should be confirmed and cross checked against the subject identifiers on the study drug packaging. SBT777101 will be infused intravenously. The subject must be continually monitored during the infusion.

Please see Section 8.1 for details and guidance on the management of potential and theoretical adverse events for SBT777101.

Please refer to the Investigational Product Manual for details on administration of SBT777101.

6.9. Continued Access to Study Drug After the End of the Study

SBT777101 will not be provided to subjects after they complete the treatment period.

6.10. Overdose or Medication Error

For this study, any dose of SBT777101 greater than that designated in the cohort the subject was assigned to will be considered an overdose.

In the event of an overdose, the study site Investigator should:

- Treat all symptoms, as appropriate, and provide supportive care
- Contact the medical monitor immediately
- Closely monitor the subject for any AE/SAE and laboratory abnormalities
- Document the quantity of the excess dose as well as the duration of the overdose
- Obtain a serum sample for PK analysis as soon as practicable

Subjects who receive an overdose or for whom there is a medication error should remain in the study and continue to complete the study assessments.

6.11. Method of Treatment Assignment and Blinding

This is an open-label study; all subjects will be treated with SBT777101. After a subject has provided informed consent, they will be provided with a unique screening number.

The Investigator, study site personnel, the laboratories assigned to analyze PK, PD, and ADA samples and all subjects will know the treatment allocation during the study. The Sponsor and designees will also know the treatment and dose that each subject receives.

7. STUDY ASSESSMENTS AND PROCEDURES

Study procedures and their timing are summarized in the SoA (see Appendix A and Appendix B). Adherence to the study design requirements, including those specified in the SoA, is essential and required for study conduct.

Safety concerns should be discussed with the Sponsor immediately upon occurrence or awareness to determine if any action is required.

All screening evaluations must be completed and reviewed to confirm that potential subjects meet all eligibility criteria. The Investigator will maintain a screening log to record details of all subjects screened and to confirm eligibility or record reasons for screening failure, as applicable.

Repeat or unscheduled blood samples may be taken for safety reasons or if technical issues occur (e.g., blood sample hemolysis) at any study visit.

7.1. Study Visits

All study assessments will be performed as described in the SoA (Appendix A and Appendix B).

7.1.1. Screening

The screening period for a subject commences at the point at which they sign the informed consent form (ICF). The subject must sign and date the ICF before any screening procedures or study-specific tests can be performed.

All consenting subjects will be given a unique subject ID number. This number will be used to identify the subject throughout the study and must be used on all study documentation related to that subject.

Subjects will be screened for study eligibility according to the assessments described in the SoA. Select data obtained during screening will be evaluated by the Sponsor to confirm study eligibility. Once full eligibility has been confirmed the subject may be enrolled into the study.

Screening is expected to last approximately 2 weeks.

7.1.2. Pre-treatment

Upon enrollment, subjects will enter the pre-treatment phase of the study. The apheresis procedure, SBT777101 manufacturing, synovial biopsy and/or fluid collection and pre-infusion eligibility checks will take place during this study period.

The pre-treatment phase is expected to last approximately 6-8 weeks.

7.1.2.1. Apheresis

An apheresis procedure will be performed on each subject to collect peripheral blood mononuclear cells (PBMCs) required for the manufacturing of SBT777101.

The collection will be performed according to Apheresis Collection Manual using standard collection procedures at a Sponsor qualified collection center and utilizing FDA approved equipment for the collection of mononuclear cells. The apheresis product should be handled per local institutional policies and procedures, in accordance with applicable regulations (including but not limited to 21 CFR 1271.145) and Occupational Safety and Health Administration (OSHA) Universal Precautions. Please refer to local site guidance for the details of criteria that need to be met before a subject can undergo apheresis.

The apheresis product will be packaged and shipped as described in the Apheresis Collection Manual.

Should technical issues arise during the apheresis procedure or during the manufacturing of SBT777101, the subject may undergo a second collection procedure with Sponsor approval. Subjects must repeat the pre-apheresis assessments to confirm that they are eligible to undergo a second apheresis procedure.

7.1.2.2. SBT777101 Manufacturing

SBT777101 study drug product will be manufactured according to the Sponsor defined process.

7.1.2.3. Synovial Biopsy and Fluid Collection

The biopsy to collect synovial tissue and/or synovial fluid prior to infusion will take place after the subject has undergone enrollment into the study. This procedure must be completed at least one week prior to the planned dosing date.

Ultrasound evaluation of joints (e.g., knees, wrists and ankles) may be performed at the same time as the synovial biopsy procedure/synovial fluid collection to assess baseline condition and pathophysiological changes following dosing with SBT777101.

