7.1.2.4. Pre-Infusion Eligibility Confirmation

Subject eligibility must be reconfirmed between study Days -10 and -4 to confirm that it is safe and appropriate that the subject receives study drug.

If any of the eligibility criteria are not met the subject must not be dosed with SBT777101. In this case, the subject remains enrolled but will need to be reassessed according to the pre-infusion eligibility criteria before dosing. Subjects can be reassessed for up to 6 months after enrollment. A subject that is not dosed within 6 months of being enrolled will be withdrawn from the study. A second apheresis is not required for subjects who qualify for infusion upon reassessment and have an available SBT777101 cell product that met the release criteria.

Subjects with active infections during the pre-treatment period should not be dosed until at least four weeks after completion of IV antibiotics and two weeks after completion of treatment with oral antibiotics/anti-infectives.

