13. APPENDICES

APPENDIX A. SCHEDULE OF ASSESSMENTS: SCREENING AND PRE-TREATMENT PERIODS

	Screening	Pre-Treatment					
Study Week	-8 to -7	-6 to -1					
Study Day (visit window)			-10 to -4				
Procedure							
Informed consent	•						
Assign Allocation Number (Subject ID)	•						
Eligibility criteria	•		•				
Demographics	•						
Medical history	•	•	•				
Prior/Concomitant medications	•	•	•				
Vital signs	•	•	•				
Full physical exam	•						
Directed physical exam			•				
Height	•						
Weight	•		•				
12-lead triplicate ECG	•						
Chest X-ray	•						
Assessment of synovitis (clinical and/or ultrasound)	•	•	•				
Joint evaluation for biopsy	•						
Synovial biopsy for tissue ^a		•					
Synovial fluid collection ^a		•					
Vein assessment	•						
Apheresis		• b					
Infectious disease serology ^c	•						
TB screening ^c	•						
Serum pregnancy test	•		•				
Lipid tests ^c			•				
Coagulation ^c	•		•				
Hematology ^c	•		•				
Clinical chemistry ^c	•		•				
Urinalysis ^c	•		•				
Markers of inflammation			•				
CRP	•		•				
Joint count assessment (28 SJC and 28 TJC)			•				
Joint count assessment (66 SJC and 68 TJC)	•						
Physician VAS	•		•				
Subject VAS (global and assessment of pain)	•		•				
HAQ-DI	•		•				
FACIT-F			•				

	Screening	Pre-T	reatment
Study Week	-8 to -7	-6	to -1
Study Day (visit window)			-10 to -4
Procedure			
Blood samples for PK (ddPCR)			•
Blood sample for cellular immunogenicity			•
Blood sample for ADA			•
Blood sample for exploratory inflammatory markers			•
Blood sample for ACPA/RF			•
Blood sample for VICM			•
Blood samples for exploratory biomarkers			•
Blood samples for RCL			•
Adverse events d	•	•	•

ACPA = anti-citrullinated protein antibody; ADA = anti-drug antibody; APH = apheresis; CRP = C-reactive protein; ddPCR = droplet digital polymerase chain reaction; ECG = electrocardiogram; FACIT-F = Functional Assessment of Chronic Illness Therapy – Fatigue; HAQ-DI = health assessment questionnaire disability index; PK = pharmacokinetic; RCL = replication competent lentivirus; RF = rheumatoid factor; SJC = swollen joint count; TB = tuberculosis; TJC = tender joint count; UV = unscheduled visit; VAS= visual analogue score VICM = citrullinated and MMP degraded vimentin fragment

- ^a Synovial biopsy and/or synovial fluid collection during the Pre-treatment period should be performed after enrollment and at least one week prior to the planned dosing visit.

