- ^b Apheresis should be scheduled and performed as soon as possible once screening eligibility is confirmed and the subject enters the Pre-Treatment period. The synovial biopsy should be done after apheresis.
- ^c Tests included in laboratory assessments are described in protocol Appendix C. Fasting glucose should be collected at the pre-treatment visit and as clinically indicated.
- ^d After informed consent has been obtained but prior to initiation of study drug, only SAEs caused by a protocol-mandated intervention should be reported.

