ACPA = anti-citrullinated protein antibody; ADA = anti-drug antibody; CRP = C-reactive protein; ddPCR = droplet digital polymerase chain reaction; ECG = electrocardiogram; ES = End of Study; ET = early termination; FACIT-F = Functional Assessment of Chronic Illness Therapy – Fatigue; HAQ-DI = health assessment questionnaire disability index; PK = pharmacokinetic; RCL = replication competent lentivirus; RF = rheumatoid factor; SJC = swollen joint count; TJC = tender joint count; UV = unscheduled visit; VAS= visual analogue score VICM = citrullinated and MMP degraded vimentin fragment

Note: On Day 1, all assessments should be performed prior to dosing, unless otherwise specified.

- ^a Subjects should be contacted daily by the site (e.g by phone or text) following discharge through Day 7.
- ^b Vital signs must be measured approximately 15 minutes prior to infusion, then approximately every 15 minutes during the infusion.
- ^c After informed consent has been obtained but prior to initiation of study drug, only SAEs caused by a protocol-mandated intervention should be reported. After initiation of study drug, all AEs will be reported until the end of the study. After this period, the Sponsor should be notified if the investigator becomes aware of any SAE that is believed to be related to prior study drug treatment
- ^d The synovial biopsy/fluid collection can be performed at or up to 1 week after the scheduled assessment visit.
- ^e The timing of the synovial biopsy and/or synovial fluid collection in may be changed based on evaluation of data from the first dose escalation cohort.
- $^{\rm f}$ The synovial biopsy sample/fluid collection at Week 12 and at the ET visit is optional.
- g Tests included in laboratory assessments are described in protocol Appendix C.
- ^h A sample to test for markers of inflammation should be collected within 30 minutes of the onset of a suspected adverse event of infection or CRS.
- ⁱ The PK sample collected on study Day 2 should be collected at approximately the same time of day that the infusion of study drug took place on study Day 1 (+/- 1 hour). An unscheduled PK sample should be collected within 30 minutes of a suspected infusion related reaction adverse event.

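### Nothing orders the pre-dose synovial biopsy against the Day -10 to -4 visit, so the last pre-dose 28-joint count, VAS, HAQ-DI and CRP may be taken 1 to 6 days after the procedure

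*Protocol*

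**What the plan says.** **Pre-dose procedure.** Section 7.1.2.3 gives the latest time: "This procedure must be completed at least one week prior to the planned dosing date". Appendix A footnote a says the collection "should be performed after enrollment and at least one week prior to the planned dosing visit", and footnote b adds "The synovial biopsy should be done after apheresis".

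**Pre-infusion visit.** Section 7.1.2.4: "Subject eligibility must be reconfirmed between study Days -10 and -4". In Appendix A this is the only pre-dose visit with the row "Joint count assessment (28 SJC and 28 TJC" ticked. It also carries physician and subject VAS, HAQ-DI and CRP. Appendix B ticks none of these on Day 1, so these are the last pre-dose values. The 66/68-joint count is ticked pre-dose at screening only, together with VAS, HAQ-DI and CRP.

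**Post-dose procedure.** Appendix B footnote d: "The synovial biopsy/fluid collection can be performed at or up to 1 week after the scheduled assessment visit". The scheduled visit is Day 28.

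**Uses of the pre-dose values.** Section 9.4.2.4 lists change from baseline in DAS28 without naming the baseline visit. Section 5.2.4 does name one: "Rescue therapy is permitted if a subject experiences ≥30% worsening in TJC and/or SJC compared to study Day -10 to -4".

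**NSAIDs.** Table 2 says that before the pre-dose biopsy they "should not be used in the 7 days prior to the synovial biopsy collection where possible". It sets a like restriction before the post-dose tissue collection.

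**The concern.** The procedure is bounded relative to enrollment, apheresis and dosing, but not relative to the visit at which disease activity is scored. A site may biopsy or aspirate a joint and score the subject a few days later. Soreness could raise the tender count, pain and global scores; removing fluid could lower the swollen count.

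After dosing the schedule works the other way: scores come first and the procedure follows. A transient procedure effect would therefore enter only the pre-dose side of a DAS28 comparison, and its resolution would read as change after treatment. The study is open-label with no control group, so nothing in the data would separate the two. The 5.2.4 reference count is exposed however the efficacy baseline is later defined.

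**Working it through.** The plan gives no figure for this point. The check is of the permitted dates, then of how sensitive the scores are.

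**1. Pre-dose gap.** Inputs: procedure at least 7 days before dosing (7.1.2.3); visit on Days -10 to -4 (7.1.2.4); dosing on Day 1 (7.1.3). The protocol does not say whether a Day 0 exists. Assume none, so Day -k is k days before dosing.

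- Gap = (days from biopsy to dosing) - (days from visit to dosing). A positive gap means the scores follow the biopsy.
- Biopsy on Days -10 to -7 (4 days) and visit on any of 7 days: 4 x 7 = 28 permitted pairs, with gaps from 7 - 10 = -3 to 10 - 4 = +6.
- Pairs with a gap of +1 to +6: 3 + 4 + 5 + 6 = 18. Pairs with the visit on the same day or earlier: 4 + 3 + 2 + 1 = 10.
- A gap of 1 to 6 days is reachable for a biopsy 7 days before dosing (visit 4 to 6 days before) up to 16 days before (16 - 10 = 6). With a Day 0 the range is 7 to 17 days, and 20 of 35 pairs give +1 to +6.
- Earlier biopsies give longer gaps: a biopsy 42 days before dosing gives up to 42 - 4 = 38 days.

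These pairs count what is allowed. They are not probabilities.

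**2. Post-dose gap.** Inputs: Appendix B windows and footnote d.

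- Latest Week 4 biopsy: Day 28 + 2 + 7 = Day 37.
- Next joint count is Week 8, at the earliest Day 56 - 2 = Day 54. Gap: 54 - 37 = 17 days.
- If the biopsy is at the Week 4 visit itself, the preferred order in Section 7.3 puts it last, after the clinical assessments. That order applies within a visit and does nothing across days.
- CRP alone is also drawn at Week 6, at the earliest Day 40, which is 3 days after Day 37. No joint count is scheduled there, so no DAS28 arises.

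Footnote e lets the timing of collection change after the first cohort, so the 17 days hold for the schedule as written.

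**3. DAS28 sensitivity.** Assumption: standard DAS28-CRP weights, 0.56 x sqrt(TJC) and 0.28 x sqrt(SJC). The counts are illustrative.

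| TJC | SJC | One more tender joint | One more swollen joint | Both |
|---|---|---|---|---|
| 3 to 4 | 2 to 3 | 0.56 x (2.000 - 1.732) = 0.150 | 0.28 x (1.732 - 1.414) = 0.089 | 0.239 |
| 6 to 7 | 4 to 5 | 0.56 x (2.646 - 2.449) = 0.110 | 0.28 x (2.236 - 2.000) = 0.066 | 0.176 |
| 15 to 16 | 10 to 11 | 0.56 x (4.000 - 3.873) = 0.071 | 0.28 x (3.317 - 3.162) = 0.043 | 0.114 |

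A joint already tender and swollen adds nothing to either count.

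**4. Rescue reference.** Smallest whole count at or above 1.3 x reference, for an assumed true count of 6:

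- recorded as 6: 7.8, so 8 joints;
- recorded as 7: 9.1, so 10 joints;
- recorded as 5 (if the procedure lowered the count): 6.5, so 7 joints.

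**The case against.** The strongest case against is that this is an edge case in an exploratory endpoint, and much of it stands.

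- Appendix A shows the biopsy in its own pre-treatment column, and Section 7.1.2 gives that phase about 6 to 8 weeks. A short gap needs a late biopsy. This stands: the gap is permitted, not planned.
- A reader might infer that the ACR baseline is equally affected. The documents do not support that for Week 12. The only post-dose 66/68 count is at Week 12, and its pre-dose match is at screening, before any biopsy, with VAS, HAQ-DI and CRP alongside. Exposure remains only where an ACR calculation takes Day -10 to -4 values, for example with 28-joint counts at other visits.
- A reader might infer that NSAID withdrawal affects baseline alone. It does not. The restriction applies only where feasible, ends at the biopsy, and recurs before the post-dose collection, so the Week 4 scores can fall inside it.
- A reader might infer that baseline is inflated. No document gives the size or direction of a procedure effect. Section 7.2.7.1 requires confirmed synovitis in the joint considered for biopsy. If that joint is already swollen, only the tender-joint term is left; if it is tender too, the counts do not move. Aspiration could lower the score.
- DAS28 above 3.1 is an entry criterion, so a DAS28 from before the biopsy should exist at screening, and the analysis plan may name it as baseline. This stands for DAS28 change. It does not help the rescue reference, which 5.2.4 fixes at Day -10 to -4.

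What the objection does not reach is the missing order. An analysis plan can choose among recorded values, but it cannot undo a count taken days after a procedure.

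**Conclusion.** The gap is real and small. The protocol permits the last pre-dose 28-joint count, VAS, HAQ-DI and CRP to be taken 1 to 6 days after the synovial procedure, while post-dose joint counts either precede the procedure or follow it by at least 17 days. Any procedure effect on DAS28, in either direction, is therefore confined to the pre-dose side.

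Two things are exposed: DAS28 change, on the condition that Day -10 to -4 serves as baseline, and the tender and swollen reference count in 5.2.4, without that condition.

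The true size is unknown. One joint could shift DAS28 by 0 to about 0.24 under the assumed weights and counts. With a true count of 6, an error of one joint moves the 30% threshold from 8 joints to 10 or to 7.

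Severity is minor: efficacy is exploratory, the sample size has no statistical basis (9.1), and the rescue options in Table 3 begin only after Week 12.

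**What to change.** In Section 7.1.2.3 and Appendix A footnote a, add one rule: the pre-infusion joint counts, physician and subject VAS, HAQ-DI and CRP are completed before the pre-dose biopsy or fluid collection (same day allowed, scores first, as after dosing), or the procedure is done early enough to leave a stated minimum interval before that visit. The sponsor should justify the interval, since the documents give no basis for a number. As an illustration, at least 7 days for every visit day would need a biopsy at least 10 + 7 = 17 days before dosing (18 with a Day 0).

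The reference visit in 5.2.4 should then be reconciled with this rule. Nothing is proposed here about the trigger or the rescue options.

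The cost is a scheduling constraint, with no added visit or procedure. Scoring first leaves Days -10 to -7 for both steps (Days -10 to -6 with a Day 0), and those scores may fall inside the NSAID restriction, as Week 4 already can. Concomitant medication is recorded at these visits, so NSAID use can be seen. Sites that biopsy soon after apheresis would usually meet the second option without change.
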